1.4.2 Risks

[Table 1](#) provides an overview of the potential risks related to exposure to the trial investigational medicinal product (BI 1569912), known risks related to the compound class, known risks related to psychoactive drugs, and trial procedure-related risks. For further details on treatment-related risks, refer also to Section [1.2](#) of the current clinical trial protocol (CTP) and the current version of the IB [[c29289852](#)].

Table 1 Overview of trial related risks

Possible or known risks of clinical relevance for this trial	Summary of data, rationale for the risk	Mitigation strategy
Investigational Medicinal Product – BI 1569912		
Nonclinical data:		
[REDACTED]		

Possible or known risks of clinical relevance for this trial	Summary of data, rationale for the risk	Mitigation strategy
Healthy volunteer data:		

Phase I SRD 
Up to [REDACTED], no AE occurred more than once across all 7 dose groups.
 
[REDACTED] 
[REDACTED]
 
Therefore, no specific AE risk associated with BI 1569912 has been identified.
 
There might be compound-related unknown risks at the same dose levels in participants with a psychiatric disorder.
	
All reported AEs were transient and a majority were of mild intensity.
 
None of the participants experienced any serious adverse events (SAEs) or relevant alterations in laboratory parameters, vital signs, or ECG.
 
Whether participants with MDD show a different sensitivity to BI 1569912 compared with healthy volunteers is not known, although a higher sensitivity is not expected. However, the doses required for efficacy might be higher than expected based on animal data using the forced swim test as a sign of potential antidepressant activity. In the first [REDACTED] participants with MDD in the ongoing PoCP clinical trial (1447-0003), no SAEs, AESIs, or adverse events of severe intensity have been observed.
	
Extensive standard safety laboratory measurements, ECG measurements, monitoring of vital signs, and physical examinations will be performed before IMP administration and at every site visit thereafter. Management of symptoms, evaluation, and follow-up will be conducted as needed to ensure participant safety, per the investigator's clinical judgement.

Possible or known risks of clinical relevance for this trial	Summary of data, rationale for the risk	Mitigation strategy
Drug-induced liver injury (DILI)	Rare but severe event, thus under constant surveillance by sponsors and regulators.	Timely detection, evaluation, and follow-up of laboratory alterations in selected liver laboratory parameters to ensure the safety of trial participants.
General risks of psychoactive drugs		
Occurrence or increase of suicidality	Some patients with MDD have an increased risk of suicidality. Some studies have shown a correlation of increased suicide risk with the use of certain antidepressants. Although there is no precedent from clinical data implicating an association between NR2B negative allosteric modulation and suicidal ideation and behaviour, this risk cannot be ruled out completely.	Participants with a recent history of clinically significant suicidal ideation are to be excluded from the current trial (refer to Section 3.3.3). In the interest of ensuring participant safety, trial participants will be proactively screened and monitored throughout the trial for suicidal ideation and behaviour in accordance with regulatory guidance.

Possible or known risks of clinical relevance for this trial	Summary of data, rationale for the risk	Mitigation strategy
Sedation, combined with impaired thinking, judgement, and/or motor skills	Psychoactive drugs are known to potentially cause unwanted side effects on brain function.	It is recommended to monitor participants for 2 h after first dose. During site visits, participants will be continuously monitored for AEs and neurological examinations will be performed throughout the trial. While no AEs involving somnolence, vision impairment, or psychomimetic effects associated with BI 1569912 have been observed in clinical trials, participants should be cautioned about operating machinery, including automobiles, until they are reasonably certain that the IMP does not adversely affect their ability to engage in such activities. It is recommended that participants should exercise caution when driving or operating machinery.
Potential compound class effects:		
Dissociative symptoms	NMDA antagonists, in particular ketamine, and some NR2B-specific modulators such as traxoprodil, are associated with the occurrence of dissociative symptoms which would be expected to occur in a dose-dependent manner.	Participants with a history of psychotic episodes or positive drug screening are to be excluded from the current clinical trial (See Section 3.3). IMP should be administered in quiet ambient conditions. Clinical assessment of psychiatric symptoms associated with dissociation will be assessed during the course of the study via the [REDACTED] AE reporting to monitor and assess the severity of specific symptoms.
Blood pressure increase	Same risk and rationale as dissociative symptoms	Monitoring of arterial blood pressure at site visits
Potential for drug abuse	Some drugs, including ketamine, are associated with a risk of abuse. While the potential for abuse liability with BI 1569912 appears low based on the currently available nonclinical data, specific clinical abuse liability studies have not yet been performed with BI 1569912.	Participants with a history of substance use disorders are to be excluded from the current clinical trial, clinical assessments of psychiatric symptoms will be conducted throughout the trial [REDACTED]

Possible or known risks of clinical relevance for this trial	Summary of data, rationale for the risk	Mitigation strategy
Matching placebo to BI 1569912		
Worsening of depression and/or the occurrence or increase in suicidality	Even though mitigation measures are applied, this risk cannot be ruled out completely.	Participants will remain on stable psychotherapy, where applicable. Participants will be monitored during the treatment and follow-up periods to ensure that worsening of pre-existing conditions or any newly occurring events are detected and any necessary actions taken according to stopping criteria.
Trial procedures		
General discomfort	Participants might experience some general discomfort due to the procedural nature of clinical trial conduct	Management of discomfort, evaluation, and follow-up will be conducted as needed to ensure participant safety.
Blood draw	The potential risks of a blood draw include fainting, pain, bruising, swelling, or infection (rarely) where the needle is inserted. In rare cases, a nerve may be damaged, inducing long-lasting abnormal sensations (paraesthesia), impaired sensation of touch, and persistent pain. The total volume of blood withdrawn during the entire study per participant will not exceed the volume of a normal blood donation (approximately 500 mL).	No health-related risk is expected from blood withdrawal.
Other risks		
Hypersensitivity and allergic reactions	As with all drugs, the potential for hypersensitivity and allergic reactions has to be taken into consideration with BI 1569912 administration.	First dosing of BI 1569912 will be conducted on site with a recommendation of at least 2 h of post-administration surveillance; monitoring and management of symptoms and treatment as needed throughout the course of the trial, including discontinuation of trial participation as per the investigator's clinical judgement.

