	
Main Exclusion Criteria:
 
• Have ever met diagnostic criteria for schizophrenia, schizoaffective disorder, schizophreniform disorder, bipolar disorder, or delusional disorder• Diagnosis with antisocial, paranoid, schizoid or schizotypal personality disorder, or MDD with psychotic features at the time of screening visit. Any other personality disorder that significantly affects current psychiatric status and likely to impact trial participation, as per the judgement of investigator• Diagnosis of any other mental disorder that was the primary focus of treatment within 6 months prior to screening, as per clinical discretion of the investigator• Treatment failure to 2 or more antidepressants in the current episode• A current or recent history of clinically significant suicidal ideation with intent within the past 3 months or a suicidal attempt within the past year• Participants with a body mass index (weight [kg]/height [m]²) lower than 18 kg/m² or greater than 40 kg/m² at screening• Diagnosis of a moderate to severe substance related disorder within 6 months prior to screening visit (with exception of caffeine and tobacco)• Frequent use of benzodiazepines• Positive drug screen (amphetamines, opiates, cocaine, barbiturates, phencyclidine) at screening. Participants with positive cannabis and benzodiazepine tests can be included if the investigator confirms that there is no moderate to severe substance related disorder or chronic benzodiazepine use• Have started psychotherapy or other non-drug therapies (e.g. acupuncture, hypnosis) within 3 months prior to screening or plan to start at any time during the study• Use of NMDA inhibitors (including ketamine/esketamine) for the current ongoing depressive episode or any past treatment failure with ketamine• Use of psychotropic medication (including antidepressant and antipsychotic therapy) which was not discontinued at least 5 half-lives prior to randomisation• Prior use of any investigational product within 6 months prior to randomisation• Have failed a 3rd party eligibility assessment within the 6 months prior screening• Known history of HIV infection and/or a positive result for an active Hepatitis B or C infection

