3.3.2 Inclusion criteria

For inclusion in the randomised trial, all inclusion criteria must be satisfied prior to randomisation.

[figure not shown]
1. Male and female participants, 18 to 65 years of age, both inclusively at the time of consent
2. Signed and dated written informed consent in accordance with ICH-GCP and local legislation prior to admission to the trial
3. Women of childbearing potential (WOCBP) must be ready and able to use a highly effective method of birth control per ICH M3 (R2) that results in a low failure rate of less than 1% per year when used consistently and correctly plus one additional barrier method. A list of contraception methods meeting these criteria and instructions on the duration of use is provided in the participant information and in Section [4.2.2.3](#)

4. Established diagnosis of MDD, single episode or recurrent, as confirmed at the time of screening by the MINI with a duration of the current depressive episode ≥ 8 weeks AND ≤ 24 months at the time of randomisation
5. Hamilton Depression Rating Scale-17 (HDRS-17) – Severity scale score ≥ 20
6. Clinical Global Impression- Severity Scale (CGI-S) score ≥ 4

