3.3.3 Exclusion criteria

All exclusion criteria must be assessed during the screening visit (Visit 1).

1. Per MINI, have ever met diagnostic criteria for schizophrenia, schizoaffective disorder, schizophreniform disorder, bipolar disorder, or delusional disorder
2. Diagnosis with antisocial, paranoid, schizoid or schizotypal personality disorder, or MDD with psychotic features as per DSM-5 criteria, at the time of screening visit. Any other personality disorder at screening visit that significantly affects current psychiatric status and likely to impact trial participation, as per the judgement of investigator
3. Diagnosis of any other mental disorder that was the primary focus of treatment within 6 months prior to screening (as per clinical discretion of the investigator)
4. Treatment failure to 2 or more antidepressants in the current episode, defined as less than 50% response to treatments administered at an adequate dose and duration as evaluated by the ATRQ
5. History or presence (upon clinical examination) of seizure disorders or an increased risk of seizures (first degree relative with epilepsy), stroke, brain tumour, or any other major neurological illness that could impact participation in the trial
6. A current or recent history of clinically significant suicidal ideation with intent within the past 3 months, corresponding to a score of 4 or 5 for ideation on the C-SSRS or a suicidal attempt within the past year, as indicated by the C-SSRS at screening visit
7. Participants with a body mass index (weight [kg]/height [m]²) lower than 18 kg/m² or greater than 40 kg/m² at screening
8. Diagnosis of a moderate to severe substance related disorder as defined by DSM-5 criteria within 6 months prior to screening visit (with exception of caffeine and tobacco)
9. Frequent use of benzodiazepines defined as use on ≥ 4 days per week within the 4 weeks prior to screening
10. Positive drug screen (amphetamines, opiates, cocaine, barbiturates, phencyclidine) at screening. Participants with positive cannabis and benzodiazepine drug tests can be included if the investigator confirms that there is no moderate to severe substance related disorder or chronic benzodiazepine use

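### Table 1 relies on excluding past psychotic episodes to limit dissociation, but on the visible criteria a resolved psychotic depressive episode does not bar entry

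*Protocol*

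**What the plan says.** Protocol Section 1.4.2, Table 1, treats dissociation as a class risk of NMDA antagonists and some NR2B modulators, expected to depend on dose. The first mitigation listed is an eligibility rule with no time limit, referring to Section 3.3: "Participants with a history of psychotic episodes or positive drug screening are to be excluded from the current clinical trial".

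The operative text on psychosis is in Section 3.3.3 and the synopsis:

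- Criterion 1 is a lifetime exclusion, applied through the MINI, of anyone found to "have ever met diagnostic criteria for schizophrenia, schizoaffective disorder, schizophreniform disorder, bipolar disorder, or delusional disorder".
- Criterion 2 covers certain personality disorders and "MDD with psychotic features as per DSM-5 criteria, at the time of screening visit".
- The synopsis words the second item in the same way: "MDD with psychotic features at the time of screening visit".

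Section 3.3.2, inclusion criterion 4, sets no condition on the type of earlier episodes: "Established diagnosis of MDD, single episode or recurrent, as confirmed at the time of screening by the MINI".

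**The concern.** The risk table and the eligibility criteria should describe the same population. Table 1 excludes any past psychotic episode. The criterion that deals with psychotic depression, the form of psychosis closest to this population, is worded around the screening visit. If nothing else closes the gap, the benefit-risk assessment counts a safeguard that the criteria do not fully contain.

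The safeguard matters because most dosing is unsupervised. Section 6.2.2.6 plans 42 days of once-daily dosing, and the schedule of assessments has site dosing at Visits 2, 3, 4 and 5. That leaves 42 − 4 = 38 planned doses at home. Staff can ensure quiet conditions only for the site doses, and the recommended 2 h of monitoring applies to the first dose. Psychiatric assessment and AE reporting detect symptoms but do not prevent them. Of the measures listed for dissociation, eligibility is the preventive one that reaches the home doses.

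**Working it through.** This is a check of text against text. The plan gives no figure to reproduce.

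**Test case.** A participant has recurrent MDD. An earlier episode had psychotic features and resolved. The current episode is non-psychotic and has lasted between 8 weeks and 24 months. None of the criterion 1 disorders was ever present, and all other criteria are met.

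**Visible criteria.**

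1. Inclusion criterion 4 admits recurrent MDD, so the participant passes.
2. Exclusion criterion 1 names 5 lifetime disorders, of which 0 is psychotic depression. The participant passes.
3. Exclusion criterion 2 is the only one of the 10 visible exclusion criteria that names MDD with psychotic features. Read as current status, it does not apply.
4. Exclusion criterion 3 reads "Diagnosis of any other mental disorder that was the primary focus of treatment within 6 months prior to screening". It concerns a disorder other than MDD and looks back 6 months, so it does not apply.
5. Criteria 4 to 10 deal with other matters.

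Table 1 says this participant is excluded, and no visible criterion does so.

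**Downstream checks.** Section 5.6.1.1 has the MINI exclude disorders according to the exclusion criteria. The external reviewer's queries in Section 6.2.1.7 relate to the same criteria and to diagnosis and severity. Section 3.3 defines randomisation in error by the same criteria. None of these adds a separate exclusion for past psychosis.

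**Criteria that cannot be seen.** The public text of Section 3.3.3 ends at no. 10. The synopsis lists 15 main exclusions, of which 9 match visible criteria (nos. 1 to 4 and 6 to 10). The remaining 15 − 9 = 6 concern starting psychotherapy, NMDA inhibitors, psychotropic washout, prior investigational product, a failed third-party eligibility assessment, and HIV or hepatitis. None of the 6 mentions past psychosis. For earlier antipsychotic treatment the synopsis asks only for a washout: "Use of psychotropic medication (including antidepressant and antipsychotic therapy) which was not discontinued at least 5 half-lives prior to randomisation".

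This count is weak evidence about the unseen criteria. Criterion 5 (seizure risk, stroke, brain tumour, other major neurological illness) is in Section 3.3.3 but not in the synopsis, so a safety exclusion can be absent from the synopsis and still exist. A pointer the other way is that a later lifetime exclusion of psychotic episodes would make the psychotic-features clause of criterion 2 superfluous.

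**The case against.** The strongest objection is that the conclusion depends on unseen text. Section 3.3.3 continues past criterion 10, and text missing from the public document is not missing from the plan. This stands, and it is why the point is conditional and the first step is to look. Nor can the synopsis be used to rule out a later criterion.

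A reader might also infer that criterion 2 must mean current status only, because Section 3.3.3 opens by saying that every exclusion criterion is assessed at the screening visit, so that repeating the timing must limit the diagnosis. The documents do not support that inference. Criteria 6, 7 and 10 repeat the screening timing too, and criterion 6 does so while looking back 3 months and 1 year. Current status remains the natural reading, but the wording does not prove it, and a site could read the clause more broadly.

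Table 1 is also a summary that points to Section 3.3, and it is compressed elsewhere. It excludes positive drug screening although criterion 10 allows cannabis and benzodiazepine positives, and it excludes a history of substance use disorders although criterion 8 covers moderate to severe disorder within 6 months. Criterion 1 already implements a large part of the psychosis mitigation. All of this is fair and lowers the weight of the point. It does not remove it, because the cell describes a control and the text it refers to, as far as visible, does not fully provide it.

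Finally, no consequence has been shown. Table 1 reports no psychomimetic effects with the drug in clinical trials to date and does not expect higher sensitivity in MDD, although it says this is not known. Quiet dosing, psychiatric assessment, AE reporting, first-dose monitoring and external eligibility review all remain. This is accepted.

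**Conclusion.** The point holds in conditional form. On the visible text, Table 1 and Section 3.3.3 disagree about a participant with recurrent MDD and a resolved psychotic depressive episode: the table excludes the participant and the criteria do not. The gap is confined to past psychotic depression and other past psychosis outside the five disorders in criterion 1.

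Two assumptions carry this: that no criterion after no. 10 excludes past psychotic episodes, and that the psychotic-features clause of criterion 2 refers to status at screening. Both are plausible, and neither can be confirmed from the public documents.

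The size is minor to moderate. It is a consistency fix that serves participant safety. It has no effect on type I error, power, sample size or the primary analysis, and the number of participants affected cannot be estimated from the documents. A reader might infer that sites are knowingly enrolling such participants or that a harm has been identified. The documents support neither, since Table 1 is itself protocol text stating that these participants are to be excluded.

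**What to change.** First check whether a criterion after no. 10 already excludes past psychotic episodes. If one does, a cross-reference from the Table 1 cell is enough.

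If none does, reword the psychotic-features part of criterion 2, in Section 3.3.3 and in the synopsis, to *current or past MDD with psychotic features or another psychotic episode*. Leave the personality-disorder part as it is.

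If the sponsor means to admit resolved psychotic depression, the alternative is to narrow the Table 1 cell to the criterion 1 disorders plus psychotic features at screening, and to reassess the remaining dissociation risk on that basis.

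The cost is one wording amendment and a few more screen failures. The MINI is already done at screening, and Section 6.2.1.5 already records depression history, including the number of previous episodes, so at most one history item is added.

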1.4.3 Discussion

Major depressive disorder was ranked as the third highest cause of the burden of disease worldwide in 2008 by the WHO, which has projected that MDD will rank first by 2030. Both patients, caregivers, and healthcare providers are seeking more effective therapies that address the core symptoms of MDD, with a faster onset of action, a higher response rate, higher remission rate, and a more tolerable safety profile than what is currently available. NR2B-specific negative allosteric inhibitors have shown rapid efficacy in reducing depressive symptoms in multiple exploratory trials with no serious safety concerns [R17-3810, R19-0986, R22-0355, c42998816]. In contrast to other compounds with a similar mode of action, which are delivered intravenously or intranasally under medical supervision, BI 1569912 is an oral medication that allows for non-monitored, home administration. This means that BI 1569912 could be given in [REDACTED] than NMDA receptor antagonists such as esketamine.

The nature of the target and the mechanism of action of BI 1569912 is well understood. The preclinical safety package has shown a favourable profile of BI 1569912 at doses in the range of the expected human exposure. [REDACTED]

[REDACTED] Close monitoring was conducted in Phase I trials for signs indicative of these events, with no reported occurrences.

In view of the patient population expected for the current trial and the need to adequately monitor suicidality; frequent clinic visits, [REDACTED] [REDACTED] are planned to monitor participants. In addition to the standard situations, treatment should be discontinued if there are signals consistent with disease worsening as listed in Section 3.3.4.1. With regard to the mechanism of action of BI 1569912 and the AEs reported in clinical trials to date, there is no undue risk related to stopping the IMP during the treatment period or at the end of the treatment period. Considering the medical need for the development of a better tolerated and more effective treatment for patients with MDD, the expected benefit outweighs the potential risks.

In the context of the unmet medical need, anticipated benefit of BI 1569912, and available non-clinical and clinical information, the benefit-risk evaluation of the compound is favourable.

